- Drs. [name], [name], [name] or [name] will discuss various treatment modalities with patients meeting the inclusion criteria. In addition to the study treatment protocol, the following treatment options will be discussed: Rituximab and conventional duration of GC therapy (6-12 months); cyclophosphamide and conventional duration of GCs, followed by azathioprine or methotrexate. Patients will be given adequate time to ask questions related to various treatment options and to discuss the study procedures in detail.
- Informed consent will be discussed with all potential study subjects by Drs. [name], [name], [name] or [name]. In addition to the physicians, a nurse or coordinator will be available to answer patient's questions.
- Patients will be given up to seven days to consider treatment options.

V. Study Procedures

A. Study visits and data collection

1. Screening visit
 - a. Diagnosis of new onset AAV or flare with BVAS/WG ≥ 3 will be confirmed by a complete history and physical examination performed by one of the investigators.
 - b. Treatment options will be discussed with the patient and informed consent for study participants will be obtained by one of the investigators.
 - c. The following laboratory values will be obtained – complete blood count (CBC), complete metabolic panel (CMP), erythrocyte sedimentation rate (ESR), C-reactive protein (CRP), ANCA, chronic hepatitis B infection panel, HIV antibody, B-cell flow cytometry, immunoglobulin levels (IgG, IgM and IgA), urinalysis and urine pregnancy test if applicable.
 - d. Imaging as deemed necessary by the investigator
 - e. Patients will begin GC therapy at a dose selected by the investigator or the treating physician with oral prednisone 60mg or 1mg/kg (if weight less than 60kg) or intravenous methylprednisolone, up to 1g/day for three days.
 - f. Patients will be started on omeprazole 20mg daily, trimethoprim-sulfamethoxazole one single strength tablet daily, calcium citrate 500mg twice daily and vitamin D 400 units twice daily.
 - g. Prior clinical assessment (labs) within one year can be used to determine screen eligibility.
2. Study visit 1 (no later than 14 days after the screening visit)
 - a. Treatment options will be discussed with the patient and informed consent for study participants will be obtained by one of the investigators.
 - i. All screening laboratory values must be completed

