 - b. First dose of rituximab 375mg/m² administered (premedication with hydrocortisone 100mg IV, diphenhydramine 25-50mg IV or PO, acetaminophen 650mg PO)
 - c. Prednisone 60mg daily continued
 - d. Focused history and physical exam performed by one of the investigators
 - e. BVAS/WG and Vasculitis Damage Index (VDI) assessed by one of the investigators
 - f. Adverse events assessed by one of the investigators
3. Study visit 2 – one week after first study visit
 - a. Second dose of rituximab 375mg/m² administered (premedication with hydrocortisone 100mg IV, diphenhydramine 25-50mg IV or PO, acetaminophen 650mg PO)
 - b. Prednisone 60mg daily continued
4. Study visit 3 – two weeks after first study visit
 - a. Third dose of rituximab 375mg/m² administered (premedication with hydrocortisone 100mg IV, diphenhydramine 25-50mg IV or PO, acetaminophen 650mg PO)
 - b. Prednisone decreased to 40mg daily

- c. Laboratory tests – CBC, CMP, ESR, CRP, urinalysis
5. Study visit 4 – three weeks after first study visit
 - a. Final dose of rituximab 375mg/m² administered (premedication with hydrocortisone 100mg IV, diphenhydramine 25-50mg IV or PO, acetaminophen 650mg PO)
 - b. Prednisone 40mg daily continued
6. Study visit 5 – four weeks after first study visit
 - a. Patient assessed for disease response defined as:
 - i. no new disease manifestations
 - ii. no worsening of existing disease
 - iii. stable or improved BVAS/WG score
 - b. Focused history and physical exam performed by one of the investigators
 - c. Adverse events assessed by one of the investigators
 - d. Prednisone decreased to 30mg daily if disease response is achieved
 - e. Laboratory tests – CBC, CMP, ESR, CRP, ANCA, urinalysis, B-cell flow cytometry
7. Phone call – five weeks after first study visit
 - a. Phone assessment for any new or ongoing symptoms performed by one of the physicians, research nurse or study coordinator
 - b. Prednisone decreased to 20mg if no new symptoms
 - c. Schedule urgent visit if new or worsening symptoms
8. Phone call – six weeks after first study visit
 - a. Phone assessment for any new or ongoing symptoms performed by one of the physicians, research nurse or study coordinator
Prednisone decreased to 10mg if no new symptoms
 - b. Laboratory tests – BMP, ESR, CRP, urinalysis
 - c. Schedule urgent visit if new/worsening symptoms or worsening laboratories
9. Phone call – seven weeks after first study visit

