project has developed CRFs for almost all of the visits, and they are labeled by visit number (Screening visit, Visits 1-11). Specific visits may have multiple CRFs depending on the protocol-specific study procedures. With the exception of the laboratory CRF, the remaining data will be entered into the Redcap system by the clinician seeing the subjects. The plan is to have no paper worksheets and the data will be entered from the LMR clinical note by the clinicians.

B. Drugs to be used

- a. Rituximab - patients will receive rituximab according to the regimen that the FDA has approved to treat AAV (375mg/m²). They will also receive hydrocortisone 100 mg, acetaminophen 650 mg, and diphenhydramine 25 mg at the time of each infusion. These medications are administered according to Rheumatology Infusion Center or the Nephrology Infusion Center protocols to decrease the likelihood of infusion reactions. Common side effects include infusion reactions, cytopenias, and infection.
- b. Glucocorticoids – prednisone will be tapered off over eight weeks from a starting dose of 60mg or 1mg/kg, whichever is lower. At the discretion of the investigators, patients can receive methylprednisolone 1g daily via intravenous infusion for three days at the onset of treatment. For patients on stable chronic doses of prednisone (4 months or greater) prior to entering the trial, prednisone will be reduced to the chronic stable dose in order to avoid adrenal insufficiency due to rapid prednisone withdrawal.
- c. Trimethoprim-sulfamethoxazole will be prescribed for prophylaxis against pneumocystis infection. Dapsone or atovaquone can be substituted for trimethoprim-sulfamethoxazole in case of allergy or at the investigator's discretion.
- d. Omeprazole will be prescribed to prevent gastrointestinal ulceration.
- e. Calcium and vitamin D will be prescribed to prevent bone loss.

Toxicity Grading Scale

All adverse events will be recorded and classified according to the most recent version of the National Cancer Institute (NCI) Common Terminology Criteria for Adverse Events (CTCAE), published June 10, 2003. Adverse events will include those associated with glucocorticoid therapy, including hypertension, diabetes, osteoporosis, fractures, weight gain, adrenal insufficiency and others. Adverse events should be recorded and graded 1 to 5 according to the CTCAE grades provided below:

- Grade 1 = Mild adverse event
- Grade 2 = Moderate adverse event

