- Grade 3 = Severe and undesirable adverse event
- Grade 4 = Life-threatening or disabling adverse event
- Grade 5 = Death

VI. Statistical Analysis

The following variables will be collected during the study:

- Baseline variables
 - o Age
 - o Sex
 - o Disease type (GPA or MPA)
 - o ANCA type
 - o New or relapsing disease
 - o If relapsing disease - treatment prior to flare
 - o BVAS/WG
 - o VDI
- BVAS/WG at visits 1 and 5-11
- VDI at visits 9 and 11
- Laboratory data at baseline and at visits 3, 5, 6, 7, 8, 9, 10 and 11 and after phone calls at 6,9 and 16 weeks of the study
 - o CBC
 - o CMP
 - o ESR
 - o CRP
 - o ANCA
 - o Urinalysis
 - o Flow cytometry for B-cells (measured at visits 1, 5, 9, 10, 11)
 - o HACA (measured at visits 1, 9, 11)
 - o Quantitative immunoglobulins (measured at visits 1, 9 and 11)
 - o Mechanistic studies (optional) (visit 1, 9, 11)
- Prednisone dose at each visit
- Adverse events

Study endpoints

Primary endpoint (assessed at 24 weeks) - Number of patients entering remission defined as BVAS/WG = 0 and prednisone dose = 0 (or maintained at patient's stable chronic dose of prednisone in order to avoid adrenal insufficiency).

Secondary endpoints (assessed at 24 weeks)

- Number of early treatment failures defined as patients who have new or worsening disease manifestations assessed at 4 weeks after study entry
- Number of severe flares defined as flare with BVAS/WG ≥ 3 or experiencing one of the major BVAS/WG items
- Number of limited flares defined as having a new occurrence or worsening of one or more minor BVAS/WG items
- Number of patients having a disease response
- Number of patients entering partial remission
- Number of patients entering sustained remission defined as BVAS/WG = 0, prednisone dose = 0 (or maintained at patient's stable chronic dose of prednisone in order to avoid adrenal insufficiency) and no disease flares during the study period.
- Area under the curve BVAS/WG

- Total GC dose

Statistical Methods

Continuous data will be summarized using descriptive statistics (e.g., mean, standard deviation, median, minimum, and maximum). Categorical data will be assessed using the Chi-square and the Fisher exact tests as appropriate. Descriptive statistics and two-sided 95% confidence intervals will be calculated to assist in the interpretation of efficacy outcomes.

Power Analysis

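### The prednisone lines at Visits 1 and 2 omit the 1 mg/kg limit; read literally, a patient under 60 kg exceeds the protocol's own starting dose for 14 days

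*Combined protocol and SAP*

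**What the plan says.** The starting dose is set in two places.

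- Section V.A, Screening visit, item e: the investigator or treating physician chooses the initial glucocorticoid, which is "oral prednisone 60mg or 1mg/kg (if weight less than 60kg) or intravenous methylprednisolone, up to 1g/day for three days".
- Section V.B, item b (Glucocorticoids): "prednisone will be tapered off over eight weeks from a starting dose of 60mg or 1mg/kg, whichever is lower".

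For oral prednisone these amount to one rule: the lower of 60 mg and 1 mg/kg. The visit schedule then gives the doses that staff follow.

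- Study visit 1, item c, and Study visit 2, item b, both read "Prednisone 60mg daily continued", with no weight condition.
- Study visit 3, item b, two weeks after Visit 1, reads "Prednisone decreased to 40mg daily".

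Nothing later in the schedule restates the weight rule. The eligibility criteria in Section III.A set no minimum weight, so patients under 60 kg can enroll. Section VI lists "Prednisone dose at each visit" among the variables collected and total glucocorticoid dose among the secondary endpoints.

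**The concern.** For a patient under 60 kg the two visit lines and the starting-dose rule cannot both hold. Someone begun on 50 mg under the rule is told one visit later to continue 60 mg. A coordinator or covering clinician working from the visit list alone could raise the dose, or start it too high.

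A patient who begins on intravenous methylprednisolone is the clearest case. That patient may have no weight-based oral dose to continue, so the flat 60 mg at Visit 1 could be the first oral dose the schedule supplies.

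What is at stake is a small, avoidable excess of steroid in the lightest patients, in a study whose purpose is to cut steroid exposure. It could also lead to different doses for similar patients in a planned sample of 20.

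**Working it through.** The plan states no figure to reproduce here, so the check is dose arithmetic.

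**Inputs from Section V.A, visit schedule, with days counted from Visit 1**

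| Period | Daily dose as written | Days |
|---|---|---|
| Visit 1 to Visit 3 | 60 mg | 14 |
| Visit 3 to Visit 5 | 40 mg | 14 |
| Week 4 to 5 | 30 mg | 7 |
| Week 5 to 6 | 20 mg | 7 |
| Week 6 to 7 | 10 mg | 7 |
| Week 7 to 8 | 5 mg | 7 |

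**Length of the affected step.** Visit 2 falls at day 7 and Visit 3 at day 14, so the 60 mg step lasts 14 days.

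**Totals**

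- After Visit 3: 40×14 + 30×7 + 20×7 + 10×7 + 5×7 = 560 + 210 + 140 + 70 + 35 = 1,015 mg.
- Flat schedule as written: 60×14 + 1,015 = 1,855 mg.
- Under the rule, for weight W below 60 kg: W×14 + 1,015 mg.
- Excess if 60 mg is given literally: (60 − W)×14 mg.

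**Results at assumed weights**

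| Weight | Daily excess | Excess over 14 days | Weight-based 8-week total | Excess ÷ total |
|---|---|---|---|---|
| 60 kg or more | 0 mg | 0 mg | 1,855 mg | 0% |
| 55 kg | 5 mg | 70 mg | 1,785 mg | 3.9% |
| 50 kg | 10 mg | 140 mg | 1,715 mg | 8.2% |
| 45 kg | 15 mg | 210 mg | 1,645 mg | 12.8% |
| 40 kg | 20 mg | 280 mg | 1,575 mg | 17.8% |

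Relative to the daily dose under the rule, the excess is 5/55 = 9% at 55 kg, 10/50 = 20% at 50 kg, 15/45 = 33% at 45 kg and 20/40 = 50% at 40 kg.

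**Visit 3.** A patient of exactly 40 kg on the rule already takes 40 mg, so the instructed step is no decrease. Below 40 kg it would be an increase.

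**The case against.** The strongest reply is that the rule is already in force. Section V.B, item b, describes the whole eight-week taper and not only the screening dose, so it covers Visits 1 and 2. The visit lines speak of continuing a dose, and a patient on 50 mg cannot continue 60 mg. On this reading 60 mg is shorthand for the starting dose. An investigator also examines each patient at Visit 1, in a small study recruiting through one hospital. This stands as evidence of intent. It does not make the lines correct as written, and it does not fully settle the case of a patient started intravenously. Visit 2 lists only the infusion and the prednisone line, with no assessment at which a wrong dose would be noticed.

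A second reply is that the percentages depend on a narrow denominator. That is fair. Prednisone can run for up to 14 days between screening and Visit 1. Adding 14 days at 1 mg/kg lowers the shares to 70/2,555 = 2.7% at 55 kg, 140/2,415 = 5.8% at 50 kg, 210/2,275 = 9.2% at 45 kg and 280/2,135 = 13.1% at 40 kg. Optional intravenous methylprednisolone would lower them further. The excess in milligrams does not change.

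Third, few adults may weigh 40 kg or less, so the Visit 3 point will rarely apply. That also stands; it is a minor companion to the main point.

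Finally, no statistical conclusion depends on this. Doses are recorded at each visit, so total glucocorticoid dose would still reflect what was given. That is correct, and no bias is alleged.

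**Conclusion.** The point holds, as a low-severity wording error in a dosing instruction. The lines at Visits 1 and 2 contradict the protocol's own dose rule for patients under 60 kg. Taken literally, they add (60 − weight) mg a day for 14 days: 70 mg at 55 kg, rising to 280 mg at 40 kg.

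These figures assume visits on schedule, every taper step taken, and no long-standing maintenance prednisone. They leave out intravenous methylprednisolone, infusion premedication and prednisone before Visit 1. The weights are illustrative. The documents do not show how many patients would be affected, and it could be none. The protocol lets a visit be rescheduled within 10 days, so a late Visit 3 could lengthen the step.

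The primary endpoint definition, and all patients of 60 kg or more, are unaffected.

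**What to change.** - Study visit 1, item c, and Study visit 2, item b: change to *Prednisone 60 mg or 1 mg/kg, whichever is lower, daily continued*.
- Study visit 3, item b: change to *Prednisone decreased to 40 mg daily (or continue the current dose if already 40 mg or lower)*.

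The cost is one phrase at each of three visits. Because the new Visit 1 line states the dose in full, it also serves a patient coming off intravenous methylprednisolone. Design, sample size and analysis stay as they are.

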 - a. Phone assessment for any new or ongoing symptoms performed by one of the physicians, research nurse or study coordinator
Prednisone decreased to 5mg if no new symptoms
 - b. Schedule urgent visit if new or worsening symptoms
10. Study visit 6 – eight weeks after first study visit
 - a. Patient assessed for partial disease remission defined as:
 - i. no new disease manifestations
 - ii. no worsening of existing disease
 - iii. BVAS/WG < 3
 - b. Adverse events assessed by one of the investigators

- c. Prednisone discontinued (or reduced to patient's stable chronic dose of prednisone in order to avoid adrenal insufficiency) if patient meets partial disease remission criteria Omeprazole discontinued
 - d. Laboratory tests – CBC, CMP, ESR, CRP, ANCA, urinalysis, B-cell flow cytometry
11. Phone call – nine weeks after first study visit
- a. Phone assessment for any new or ongoing symptoms performed by one of the physicians, research nurse or study coordinator Laboratory tests – CBC, CMP, ESR, CRP
 - b. Schedule urgent visit if new/worsening symptoms or worsening laboratories
12. Study visit 7– twelve weeks after first study visit
- a. Focused history and physical exam performed by one of the investigators
 - b. BVAS/WG assessed by one of the investigators
 - c. Adverse events assessed by one of the investigators
 - d. Laboratory tests – CBC, CMP, ESR, CRP, ANCA, urinalysis
13. Phone call – sixteen weeks after first study visit
- a. Phone assessment for any new or ongoing symptoms performed by one of the investigators
 - b. Laboratory tests – CBC, CMP, ESR, CRP, ANCA, and urinalysis
 - c. Schedule urgent visit if new/worsening symptoms or worsening laboratories
14. Study visit 8 – twenty weeks after first study visit
- a. Focused history and physical exam performed by one of the investigators
 - b. BVAS/WG assessed by one of the investigators
 - c. Adverse events assessed by one of the investigators
 - d. Laboratory tests – CBC, CMP, ESR, CRP, ANCA, urinalysis
15. Study visit 9 – twenty-four weeks after first study visit
- a. Focused history and physical exam performed by one of the investigators
 - b. BVAS/WG and VDI assessed by one of the investigators
 - c. Primary outcome measured - defined as BVAS/WG = 0 and prednisone dose = 0 (or maintained at patient's stable chronic dose of prednisone in order to avoid adrenal insufficiency) with no preceding flares.
 - d. Adverse events assessed by one of the investigators

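### At the week 5, 6 and 7 phone calls, a patient with worsening but no new symptoms qualifies for both a prednisone cut and an urgent visit

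*Combined protocol and SAP*

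**What the plan says.** The dose rules are in Section V.A (study visits and data collection).

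- **Week 4 (item 6, Study visit 5).** "Prednisone decreased to 30mg daily if disease response is achieved". Response has three criteria. One is that nothing new has appeared; another, listed separately, is "no worsening of existing disease".
- **Week 5 call (item 7).** Scope and caller: "Phone assessment for any new or ongoing symptoms performed by one of the physicians, research nurse or study coordinator". Dose rule: "Prednisone decreased to 20mg if no new symptoms". Safety rule: "Schedule urgent visit if new or worsening symptoms".
- **Week 6 call (item 8).** Same scope and callers. Dose rule: "Prednisone decreased to 10mg if no new symptoms". Safety rule: "Schedule urgent visit if new/worsening symptoms or worsening laboratories".
- **Week 7 call (item 9).** Same scope and callers. Dose rule: "Prednisone decreased to 5mg if no new symptoms". The safety rule is worded as at week 5.
- **Week 8 (item 10, Study visit 6).** Prednisone stops only in partial remission, which again excludes worsening of existing disease as a criterion of its own.

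Under the heading on treatment of flares, worsening of a minor BVAS/WG item with a total score below 3 is a limited flare even if nothing new has appeared. A first one is treated by raising prednisone, to at most 40 mg/day for one week and then a taper. The investigator may choose a lower dose and a shorter taper.

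**The concern.** Within each call the two rules use different conditions. Worsening is asked about and leads to an urgent visit, but it does not stop the cut. The protocol does not otherwise treat worsening as a kind of new symptom: disease response, partial remission and limited flare each name the two separately, and so does the urgent-visit line itself.

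A worsening symptom reported by telephone is not necessarily a flare; the urgent visit is there to decide that. Until it happens, the written rule moves the dose in the opposite direction from the flare plan. The patient state is realistic. Entry requires BVAS/WG of at least 3 (Section III.A), and week 4 response needs only a stable or improved score, so a patient can reach week 5 with active disease that can worsen.

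The caller may be a study coordinator, who most needs an unambiguous rule. By contrast, the week 16 call (item 13), which carries no dose step, is reserved for an investigator.

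**Working it through.** The plan gives no figure of its own on this point, so the check is logical, followed by simple dose arithmetic.

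**1. Apply both rules to every symptom state.** The result is the same at weeks 5, 6 and 7.

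| New symptoms | Worsening symptoms | Dose rule | Safety rule |
|---|---|---|---|
| No | No | Cut | None |
| Yes | No | No cut | Urgent visit |
| Yes | Yes | No cut | Urgent visit |
| **No** | **Yes** | **Cut** | **Urgent visit** |

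One state of four meets both rules. At week 6 the overlap is wider, because worsening laboratories without new symptoms also meet both.

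**2. Look for text that holds the dose.** There is none. The flare provisions and the provisions on terminating the protocol apply once a flare or a failure has been established. The allowance for additional visits concerns visits, not dose. No time to the urgent visit is given.

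**3. Size of the step.** Doses are from Section V.A, items 6 to 9; 40 mg/day is the maximum for a first limited flare.

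| Call | Step (mg/day) | Cut | Gap to 40 after cut | Gap to 40 if held |
|---|---|---|---|---|
| Week 5 | 30 to 20 | 10 (10/30 = 33%) | 40 − 20 = 20 | 40 − 30 = 10 |
| Week 6 | 20 to 10 | 10 (10/20 = 50%) | 40 − 10 = 30 | 40 − 20 = 20 |
| Week 7 | 10 to 5 | 5 (5/10 = 50%) | 40 − 5 = 35 | 40 − 10 = 30 |

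**4. Planned oral prednisone, Visit 1 to week 8.** This takes a 60 mg start and excludes screening doses, intravenous methylprednisolone and premedication:

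60×14 + 40×14 + 30×7 + 20×7 + 10×7 + 5×7 = 840 + 560 + 210 + 140 + 70 + 35 = 1855 mg.

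**5. Prednisone at issue before examination.** The time to the urgent visit is assumed to be 1 to 7 days, 7 being the interval to the next scheduled contact.

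- Week 5 or 6: 10×1 to 10×7 = 10 to 70 mg; 10/1855 = 0.5% to 70/1855 = 3.8%.
- Week 7: 5×1 to 5×7 = 5 to 35 mg; 5/1855 = 0.3% to 35/1855 = 1.9%.

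These amounts are what the present rule withholds from a patient who is worsening. They are also what a hold would add for a patient whose worsening turns out not to be vasculitis.

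**The case against.** The best defence is that the protocol does not say which rule is applied first, and a careful clinician would probably hold the dose or treat worsening as something new. That is fair as a forecast of practice. It does not alter the rule: holding the dose would depart from the written schedule, and the caller need not be a clinician.

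Second, the contrast with weeks 4 and 8 is selective. The larger step at week 2, from 60 to 40 mg (item 4), has no condition at all, and weeks 4 and 8 are formal decision points for leaving the protocol. So absence of worsening is not a universal precondition for a cut. But the phone steps do carry a symptom condition, and it disagrees with the trigger beside it.

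Third, 40 mg/day is a ceiling that the investigator may undercut, and most of each gap to it would exist with the dose held. This stands. The part due to the wording is 10, 10 or 5 mg/day.

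Fourth, other provisions limit the exposure: contacts are weekly from week 4 to week 9, the week 8 stop is blocked without partial remission, severe flares go to best medical judgment, and Section I commits to longer glucocorticoid therapy where needed. These shorten the exposure to one step for a short time, but none of them withholds the cut at the call.

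Finally, patients on a stable chronic dose return to that dose (Section V.B), so some of them may not take the later steps as listed.

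**Conclusion.** The concern holds. At all three calls, a patient with worsening but no new symptoms meets the rule for a cut and the rule for an urgent visit, and nothing in the protocol says that the dose waits. The consequence is one taper step, 10, 10 or 5 mg/day, between the call and the visit. The step sizes follow directly from the schedule. The cumulative figures rest on a 60 mg start and the assumed 1 to 7 days to the visit. How often this would happen among the planned 20 patients cannot be estimated from the document. The point concerns patient safety and consistent dosing between callers; it changes neither the endpoint counts nor the analysis. It should be corrected, because following the rule as written lowers the dose in a patient who may need it raised.

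**What to change.** In Section V.A, items 7, 8 and 9, change the condition for the cut to *if no new or worsening symptoms*. Add one sentence: when a call triggers an urgent visit, the current dose is held until that visit. At week 6, if laboratory results arriving after the call trigger the visit, the dose is reviewed there. It would also help to state that, if no flare is found, the investigator decides at that visit when the deferred step is taken, with the week 8 criteria unchanged.

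The cost is a few words in three items. The downside is that patients whose worsening proves non-vasculitic stay on the higher dose until seen, which adds slightly to the secondary endpoint of total glucocorticoid dose, by no more than the 70 mg derived above. The sample size is unaffected.

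### For patients whose stable chronic prednisone dose exceeds 5 mg/day, the week 5 to 8 taper steps and section V.B.b are not reconciled

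*Combined protocol and SAP*

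**What the plan says.** Section V.A sets the prednisone dose visit by visit:

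- Visits 1 and 2 (weeks 0 and 1): "Prednisone 60mg daily continued".
- Visit 3 (week 2): "Prednisone decreased to 40mg daily". This dose is kept at visit 4 (week 3).
- Visit 5 (week 4): "Prednisone decreased to 30mg daily if disease response is achieved".
- Phone call, week 5: "Prednisone decreased to 20mg if no new symptoms".
- Phone call, week 6: "Prednisone decreased to 10mg if no new symptoms".
- Phone call, week 7: "Prednisone decreased to 5mg if no new symptoms".
- Visit 6 (week 8), if the partial remission criteria are met: "Prednisone discontinued (or reduced to patient's stable chronic dose of prednisone in order to avoid adrenal insufficiency".

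The week 8 entry is the first in the schedule to mention a chronic dose. A physician, research nurse or study coordinator may make the calls at weeks 5 to 7.

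Section V.B.b describes a taper to zero over eight weeks. It adds that, for patients who had been on a stable dose for at least four months before entry, "prednisone will be reduced to the chronic stable dose in order to avoid adrenal insufficiency due to rapid prednisone withdrawal". It ties this rule to no week.

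Section III excludes more than 14 days of prior glucocorticoid treatment but exempts patients on a stable maintenance dose at the time of the flare. It states no maximum for that dose. The primary and sustained-remission definitions accept the chronic dose in place of zero. Total glucocorticoid dose is a secondary endpoint in section VI.

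**The concern.** Just before the week 8 step the scheduled dose is 5 mg/day. A patient whose chronic dose is higher than that cannot be reduced to it from 5 mg, so the wording of the step does not match its direction. By then the schedule, followed as printed, has already taken the patient below the dose at which V.B.b says prednisone is to settle.

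Two things are at stake. The protocol gives avoidance of adrenal insufficiency as the reason for the chronic-dose rule, in both V.A and V.B.b, and lists adrenal insufficiency among the glucocorticoid-related adverse events to be recorded. A schedule that can be followed to a dose below the chronic one is hard to square with that reason. Second, staff working from V.A and staff working from V.B.b could give the same patient different doses in weeks 5 to 7, and the difference enters total glucocorticoid dose.

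**Working it through.** The plan gives no figure of its own to reproduce here, and the convenience sample of 20 plays no part. The check compares the printed weekly doses with a chronic dose D.

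**Inputs from section V.A.** Daily doses for weeks 0 to 7, with every conditional step taken: 60, 60, 40, 40, 30, 20, 10, 5 mg.

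**Assumption.** The documents give no value for D. The range used is 2.5 to 20 mg/day.

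**Scheduled eight-week total at the 60 mg start:** 7 × (60 + 60 + 40 + 40 + 30 + 20 + 10 + 5) = 7 × 265 = 1855 mg. This leaves out intravenous methylprednisolone and the hydrocortisone premedication. A patient starting at 1 mg/kg would have a lower total, but the week 5 to 7 comparison would not change.

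**Formulas.**
- Change at week 8 = D − 5.
- Weeks below D = number of weeks with a scheduled dose less than D.
- Shortfall = 7 × sum of (D − scheduled dose) over those weeks. This is also the difference in total dose between the literal schedule and a taper that stops at D.

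| Assumed D (mg/day) | Change at week 8 (mg/day) | Weeks below D | Shortfall (mg) | Share of 1855 mg | Eight-week total if the taper stops at D (mg) |
|---|---|---|---|---|---|
| 2.5 | −2.5 | 0 | 0 | 0% | 1855 |
| 5 | 0 | 0 | 0 | 0% | 1855 |
| 7.5 | +2.5 | 1 | 7 × 2.5 = 17.5 | 0.9% | 1872.5 |
| 10 | +5 | 1 | 7 × 5 = 35 | 1.9% | 1890 |
| 15 | +10 | 2 | 7 × (5 + 10) = 105 | 5.7% | 1960 |
| 20 | +15 | 2 | 7 × (10 + 15) = 175 | 9.4% | 2030 |

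Above 20 mg the week 5 step also falls below D, which adds a third week.

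**Against the 24-week total.** Section VI assesses the secondary endpoints at 24 weeks. If the patient takes D from week 8 to week 24 under either reading, both totals gain 16 × 7 × D = 112 × D. For D = 7.5 the literal total is 1855 + 840 = 2695 mg, and the difference is 17.5/2695 = 0.6%. For D = 20 it is 1855 + 2240 = 4095 mg, and the difference is 175/4095 = 4.3%.

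**Passages side by side.** The weekly steps in V.A say nothing about chronic users before week 8. V.B.b gives these users a different end point but does not say when it applies or that it displaces the weekly steps. Placing the exception at week 8 alone suggests that it does not operate earlier; V.B.b allows that it might. The documents do not settle which governs.

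**The case against.** The strongest reply is that V.B.b already deals with these patients. A general schedule followed by a special rule for a subgroup is ordinarily read with the special rule governing. On that reading the taper stops at the chronic dose and there is no conflict. The endpoint wording, which speaks of being maintained at that dose, fits this reading. This much stands: the passages are ambiguous, and a coherent reading exists. It does not close the point, because V.B.b names no week, claims no precedence, and sits apart from the list that staff making the calls would follow.

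A reader might also infer more than the documents support:

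- *That every patient is driven to 5 mg at week 7.* The week 4 step requires disease response and the week 5 to 7 steps require no new symptoms. Patients who fail response, have a severe flare or have two limited flares move to best medical judgment.
- *That the schedule defeats its own safety purpose.* That needs both the literal reading and a chronic dose above 5 mg. The documents say nothing about the clinical effect of one or more weeks below the chronic dose.
- *That the primary endpoint is distorted.* It is measured at week 24, 16 weeks after the week 8 step. The dose in weeks 5 to 7 does not determine whether the patient is at the chronic dose then.
- *That flare counts around week 8 are affected.* Symptoms reported by phone lead to an urgent visit; flares are defined by BVAS/WG items or score. No effect on the counts is shown.

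**Conclusion.** The point holds as an unreconciled conflict between the week 5 to 8 entries in V.A and V.B.b, confined to patients with a stable chronic dose above 5 mg/day who follow the taper. For them the literal schedule means at least one week below the chronic dose and an upward step at week 8 where the text describes a reduction.

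The endpoint directly touched is total glucocorticoid dose, and the effect per affected patient is modest: about 1% to 9% of the scheduled eight-week total, or about 0.6% to 4.3% of the 24-week total. These figures rest on an assumed chronic dose of 7.5 to 20 mg, a 60 mg start and every conditional step being taken. The documents give neither the number of chronic users nor their doses, so the effect on the trial as a whole cannot be sized.

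The matter still merits correction, because it concerns a dosing instruction that can be followed in two ways and a safety purpose that the protocol itself states.

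**What to change.** Reconcile the week 5, 6, 7 and 8 entries in section V.A with section V.B.b, so that both state the same rule for patients on a stable chronic dose and say how that rule relates to the weekly steps. Word the week 8 entry so that it matches the direction in which the dose changes under that rule. Which rule applies is a clinical decision for the sponsor, and none is proposed here.

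The cost is a short wording change and a cross-reference in a protocol amendment. The sample size, visits, data collected and endpoint definitions do not change.
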